#### 10.3.2 Genomic signatures extracted from biopsy

493 genes in 16 pathways that include apoptosis, base excision repair, DNA double strand break repair, homologous recombination, mismatch repair, non-

homologous end joining, hypoxia, p53 signaling, prostate cancer signaling, androgen receptor signaling, and cell cycle checkpoint (including G1/S, G2/M & mitotic spindle checkpoint) will be assessed using a 1.4 million feature oligonucleotide microarray by GenomeDx as discussed above. Some of these pathways might also be useful in determining response to treatment and it would be beneficial to understand the timing of gene expression changes occur during the AS period and how such changes relate to alterations in imaging features. We will develop a predictive model including 493 genes in 16 pathways.

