For radiomic signatures, gene signatures, and other biomarkers such as Gleason score and percent positive tissue (PPT), descriptive statistics (counts and percents; median and range; mean and standard distribution) and box plots will be used to summarize the distribution of the variables. In particular, once the habitats are defined, imaging features may be extracted. These features describe characteristics of the image intensity histograms (e.g., high or low intensity), tumor shape (e.g. round or spiculated), texture patterns (e.g. homogeneous or heterogeneous), as well as tumor location. We will consider a two-stage feature selection approach. In the first step, we will filter out "radiomics" variables using standard t-test or ANOVA and in the second step; we will perform random forests to identify radiomics signatures of habitats in relation to risk groups. Genes will be selected using Significance Analysis of Microarray (SAM) in R package, which allow the determination of significantly differentially expressed genes between classes (HP-Risk 1-4) controlling the Benjamini-Hochberg false discovery rate (FDR). The augmented classifiers predictive model will be developed using multivariate ordinal logistic regression. We will use area under the

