receiver's operating characteristic curve (AUC) with 10-fold cross-validation approach to evaluate performance of prediction model. Radiomic profiles on multi-parametric MRI that suggest regions of the prostate that are suspicious for more aggressive prostate cancer will be correlated to histopathologic findings from biopsy of these regions. Genomic profiles from tissue cores in each region will be correlated to radiomic profiles and histopathology from that region to see what each adds to improving the ability to predict patients who are likely to harbor more aggressive tumors that would portend poor outcome on active surveillance. Radiomic and genomic profiles from MRI targeted biopsies will be compared to segmental biopsies to see if profiles from targeted biopsies are more informative for risk assessment compared to segmental biopsy using longitudinal analysis approach. We will also assess how these profiles change over time in serial imaging and biopsy and see if/ how these profile changes correlate to change in histopathology. We will also relate genomic and radiomic profiles of the prostate to common serum and urinary markers that have been used predict progression on active surveillance. For continuous outcomes, association between outcome and other covariates will be examined using linear regression model and correlation coefficient. For binary outcomes and time-to-event outcomes, logistic regression and Cox proportional hazards regression will be used, respectively. All tests will be two-sided and statistical significance will be considered when  $p < .05$  after multiplicity adjustment.

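### Section 10.5 does not say that radiomic and gene selection are repeated inside the 10-fold cross-validation, or that folds are assigned by patient; run in the order described, the AUC is biased upward.

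*Combined protocol and SAP*

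**What the plan says.** Section 10.5 (Statistical Analysis) sets out the signature work in this order.

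1. Radiomic features: the plan will consider filtering out "variables using standard t-test or ANOVA and in the second step; we will perform random forests to identify radiomics signatures". These signatures describe the habitats, and the selection is made against the men's risk groups. No p-value cut-off and no number of candidate or retained features is given.
2. Genes: "Genes will be selected using Significance Analysis of Microarray (SAM) in R package", comparing four HP-Risk classes under Benjamini-Hochberg FDR control. The FDR level is not given. Section 10.3.2 sets the candidate pool: "We will develop a predictive model including 493 genes in 16 pathways".
3. Model: "The augmented classifiers predictive model will be developed using multivariate ordinal logistic regression".
4. Performance: AUC with a "10-fold cross-validation approach to evaluate performance of prediction model".

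The plan does not say which of steps 1 to 3 are repeated in each fold, or whether the unit assigned to a fold is the man, the prostate region or the biopsy core. It describes no hold-out or external validation set for this model. Section 10.5 closes with a general rule that tests are judged at p<.05 after multiplicity adjustment, without tying that rule to the radiomic filter.

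Sections 3.3 and 10.3 class the radiomic and genomic signatures as exploratory.

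**The concern.** Steps 1 and 2 both use the class labels. If they are carried out once on everyone and only the fitted model is then cross-validated, each held-out man has already helped to choose the features on which he is tested. His prediction is not out of sample, and the AUC is too high even when no feature carries information.

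The fold unit raises a separate problem. Section 10.5 analyses tissue cores by region and follows profiles over serial imaging and biopsy, and section 7.2 schedules biopsies at baseline and at 12, 24 and 36 months. One man can therefore supply several correlated samples. If folds are formed by region or core, his data can lie in both the training and the test set, whatever is done about selection.

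Cross-validation is the only safeguard described for these models. An inflated AUC could make a signature look ready for validation when it is not.

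**Working it through.** **The plan's own figure.** The documents state no AUC, so there is none to reproduce on this point. The sample size and event rate used below come from the power statement in section 10.4, which does reproduce. With 150 men, 12.5% against 25%, and an exact two-sided 5% test, the rule is to reject at 28 or more progressions. The upper-tail error is 0.0193 and the power 0.9734, against 97.3% stated.

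**Inputs from the documents.** 150 men and a 25% rate (section 10.4), so 150 × 0.25 = 37.5, about 38 events; 230 men (section 4.1); 493 genes (section 10.3.2); four classes and 10 folds (section 10.5).

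**Assumptions.** The radiomic feature count is taken as 50, 138 or 493. The figure 138 is borrowed, for illustration only, from the liver CT study described in section 1.4.3. The filter is taken as unadjusted p<.05, the FDR level as 5%, 10% or 20%, and the class shares as equal or 40/30/20/10%. Features are independent noise with one sample per man, so the true AUC is 0.5.

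**Check A: binary outcome, t-test filter, lightly penalised logistic model.** The expected number of noise features passing is 0.05 × m: 0.05 × 50 = 2.5, 0.05 × 138 = 6.9 and 0.05 × 493 = 24.7. The runs at N=150 averaged 2.4, 6.8 and 24.0.

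| Features | Selected once, N=150 | Nested, N=150 | Selected once, N=230 | Nested, N=230 |
|---|---|---|---|---|
| 50 | 0.67 | 0.50 | 0.64 | 0.51 |
| 138 | 0.74 | 0.50 | 0.71 | 0.50 |
| 493 | 0.87 | 0.49 | 0.83 | 0.50 |

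Entries are mean cross-validated AUCs. Repeating the simulation at 150 men gave 0.66 to 0.87.

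**Check B: four classes, closer to section 10.5.** ANOVA p<.05, then the ten features ranked highest by random forest, then a proportional-odds model; AUC for classes 3-4 against 1-2; N=150. There were 20 repeats with selection done once and 8 nested.

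| Class shares | Features | Selected once: mean (range) | Nested |
|---|---|---|---|
| equal | 138 | 0.61 (0.47-0.68) | 0.48 |
| equal | 493 | 0.67 (0.54-0.75) | 0.52 |
| 40/30/20/10% | 138 | 0.62 (0.48-0.71) | 0.52 |
| 40/30/20/10% | 493 | 0.68 (0.57-0.78) | 0.49 |

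**Check C: gene step.** Benjamini-Hochberg applied to test p-values stands in for SAM, with a binary outcome, 493 noise genes and 150 men. When every gene is noise, the chance of selecting any gene should equal the FDR level. The runs agree: nothing was selected in about 94%, 90% and 80% of runs at 5%, 10% and 20%. When something was selected on all men first, the AUC averaged about 0.72. A four-class version at 5% selected something in 5.8% of runs.

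**Check D: if the multiplicity rule also governed the radiomic filter.** With Bonferroni over 138 features and four classes, a noise feature passed in about 5% of runs.

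The effect of splitting one man's samples across folds was not simulated, so no figure is attached to it.

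**The case against.** The strongest reply is that the order of the prose is not the order of computation. The text never says that selection is done once on all men, and the prediction model that is cross-validated could mean the whole procedure, selection included. This stands: the plan is silent in both directions, and a reader who infers that it commits to selection outside the folds goes further than the text.

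A reader might also infer that the AUC would look strong for pure noise in general. The documents do not support that. Very high values need many candidates with a loose cut-off, or a fixed-size selection (the top 20 of 493 noise features, chosen first, gives 0.87), and the plan has no fixed-size rule. Its gene step is under FDR control and usually selects no noise gene. The general multiplicity rule, if it binds the radiomic filter, would also stop most noise there.

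Two limits remain on that reply. FDR control restricts how often false genes enter; it does not make the AUC honest when the test men helped to choose them. And no error control is stated for the random-forest step.

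Finally, Hypotheses 3 and 4 (section 2) might be thought to rest on these AUCs. They concern associations, and section 10.5 also plans correlations and linear, logistic and Cox models for such questions. The secondary AUC comparison in section 10.2.3 does not describe this selection pipeline.

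**Conclusion.** The point holds as a conditional one. Section 10.5 describes outcome-based selection before, and apart from, the cross-validation, and specifies neither nesting nor the fold unit. If the steps are run in that order, the AUC is biased upward.

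The size rests on inputs that the plan omits. Under the assumptions listed above, at 150 men, pure noise yields a mean AUC of about 0.66 to 0.87 with an unadjusted filter and a binary outcome, and about 0.61 to 0.68 in the four-class pipeline, against about 0.5 when nested. The simulated features are independent; real radiomic features are likely to be correlated, which would change the figures but not the need for nesting. In the gene step, inflation from pure noise is infrequent.

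Only the exploratory signature models are affected. The primary endpoint, the 24-month cumulative progression rate, does not use them. This is a change that should be made, not one on which the trial's main conclusion turns.

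**What to change.** Add to section 10.5 that every step using the outcome (the t-test or ANOVA filter, random-forest selection, SAM and any tuning) is refitted within each training fold, and that the AUC is computed only on men who played no part in those steps. Add that folds are assigned by patient, so that all regions, cores and serial samples from one man stay together.

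In the same place, give the number of candidate radiomic features, the filter cut-off, the FDR level, and whether the general multiplicity rule applies to the filter.

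The cost is a few sentences and more computing time, since selection runs ten times instead of once. The reported AUC will probably be lower than one obtained by selecting on all men first. No change to data collection or sample size is needed.

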## **10.6 Interim monitoring**

Since this is a single arm trial, we do not propose any planned interim analysis or early stopping guidelines.

# **11. INVESTIGATOR'S RESPONSIBILITIES**

## **11.1 Investigator Responsibility/Performance**

The investigator will ensure that this study is conducted in accordance with all regulations governing the protection of human subjects.

The investigator will ensure that all work and services described in or associated with this protocol will be conducted in accordance with the investigational plan, applicable regulations, and the highest standards of medical and clinical research practice.

## **11.2 Confidentiality**

The investigator must ensure that each subject's anonymity will be maintained and each subject's identity will be protected from unauthorized parties. A number will be assigned to each subject upon study entry and the number and the subject's initials will be used to identify the subject for the duration of the study. The investigator will maintain all documents related to this study in strict confidence.

## **11.3 Informed Consent and Permission to Use Protected Health Information**

It is the responsibility of the investigator to obtain written informed consent from each subject participating in this study after adequate explanation, in lay language, of the methods, objectives, anticipated benefits, and potential hazards of the study. The investigator must also explain that the subject is completely free to refuse to enter the study or to discontinue participation at any time (for any reason) and receive alternative

conventional therapy as indicated. Prior to study participation, each subject will sign an IRB approved informed consent form and receive a copy of same (and information leaflet, if appropriate). For subjects not qualified or able to give legal consent, consent must be obtained from a parent, legal guardian, or custodian.

The investigator or designee **must** explain to the subject before enrollment into the study that for evaluation of study results, the subject's protected health information obtained during the study may be shared with the study sponsor, regulatory agencies, and the IRB. It is the investigator's (or designee's) responsibility to obtain permission to use protected health information per HIPAA from each subject, or if appropriate, the subjects' parent or legal guardian.

#### **11.4 Source Documentation and Investigator Files**

The investigator will maintain adequate and accurate records to document the conduct of the study and to ensure that study data can be subsequently verified. These documents will be classified into two separate categories: (1) investigator study file and (2) subject clinical source documents that corroborate data collected on the CRF's. Subject clinical source documents would include hospital/clinic patient records; physician's and nurse's notes; original laboratory, radiology, pathology, and special assessment reports; QOL forms, signed informed consent forms. When the CRF or any form is used as the source document, this will be clearly stated in the investigator study file.

At a minimum, the following be documented in source documents:

- Medical history/physical condition and diagnosis of the subject before involvement in the study sufficient to verify protocol entry criteria
- Study number, assigned subject number, and verification that written informed consent was obtained (each recorded in dated and signed notes on the day of entry into the study)
- Progress notes for each subject visit
- Laboratory test results
- Condition and response of subject upon completion of or early termination from the study
- Quality of Life Surveys
- DCE-MRI tumor size and location generated by the in-house developed software

#### **11.5 Recording and Processing of Data**

Data for this study will be entered into electronic CRFs in REDCap. A CRF is required for every patient who received any study intervention. The investigator will ensure that the CRF's are accurate, complete, legible and timely. All corrections to study data will be made by drawing a single line through the information to be corrected without obscuring it. All corrections will be initialed, dated and explained, if necessary.

**Do not use "white-out" or obscuring correction tape.**

#### **11.6 Non-Protocol Research**

No investigative procedures other than those described in this protocol will be undertaken on the enrolled subjects without the agreement of the IRB.

#### **11.7 Ethics**

The investigator agrees to conduct the study in compliance with the protocol, current good clinical practices, and all applicable (local, FDA) regulatory guidelines and

standard of ethics.

### **11.8 Essential documents for the conduct of a clinical trial**

Essential documents are those documents with individually and collectively permit evaluation of the conduct of a trial and the quality of the data produced.

The following documents will be on file:

- CV's and license of all investigators
- IRB documentation/correspondance
- Documentation of IRB certification

## APPENDIX I: LIST OF STAND-ALONE DOCUMENTS

Number	Document reference number	Date	Title
1	MAX-PC	1Jun2003	The Modified 18-Item Memorial Anxiety Scale for Prostate Cancer
2	EPIC-SF12	Feb2002	The Expanded Prostate Cancer Index Composite + SF12 and AUASI
3	FFQ		Food Frequency Questionnaire (Optional-collected at baseline only)

## APPENDIX II: STUDY CALENDAR

Assessment	Screening (within 3 months of enrollment)	Baseline (within 3 months of enrollment unless otherwise specified)	Post-initial study biopsy (+1.5 months)						FU
			6 mo	12mo	18mo	24 mo	30 mo	36 mo	
Diagnostic biopsy (consisting of at least 8 cores)	X (within 18 months of enrollment & reviewed by UM Pathology)								
History & Physical Exam	X		X B	X B	X B	X B	X B	X B	
PSA	X	X (if not done within 6 mos [+1.5 mos] of initial study biopsy)	X C	X C	X C	X C	X C	X C	X A
MP-MRI of prostate/pelvis		X (+/- 3months of enrollment)		X		X		X	
MRI-guided prostate biopsy		X		X		X		X	
EPIC-SF12 & MAX-PC		X		X		X		X	
FFQ		X (optional)							
Plasma and serum collection for research (five tubes of blood, if patient has consented)		X		X		X		X	
Urine collection for research (Approximately 50 mL, post prostate massage, if patient has consented and if research funds are available)		X		X		X		X	

A: Men undergoing protocol defined progression

- Men undergoing surgery: will be followed every 3-6 months (+/- 2 months) for the first year, every 6-12 months (+/- 3 months) in the second year, and annually (+/- 6 months) thereafter up to 5 years post surgery. Any adjustments to this schedule will be permitted under the discretion of the clinician.
- Men undergoing radiation therapy: follow up serum PSA testing should occur every 6 months (+/- 3 months) for the first 3 years and then annually thereafter (+/- 6 months) for up to 5 years post treatment. If the patient enters a radiation oncology clinical trial then the timing of PSA and other labs will be timed in accordance with the radiation treatment protocol.

b History and Physical Exams will be done at the discretion of the treating physician

c Serum PSA will be done preferably every 6 months or at least once a year up to 36 months from the initial biopsy.
